### Description of Treatment Groups.

**NCI QuitGuide App + NRT Condition** The National Cancer Institute's QuitGuide app is a free smartphone app that is available on the Apple and Android app stores and has been downloaded by thousands of users. QuitGuide is one of the few apps that includes many of the recommendations detailed in the Clinical Practice Guideline. Individual level app feature use is accessible by request from the Smokefree.gov server (the PI has already obtained this type of QuitGuide data for a pilot study). The QuitGuide app aims to help smokers understand their smoking patterns and develop the skills needed to quit smoking. Participants who are randomly assigned to the QuitGuide condition will download the QuitGuide app and it will be set for a quit date 1 week following the baseline visit. QuitGuide provides content during the pre-quit period to prepare participants for their quit attempt. Participants will receive information on how to use QuitGuide app features. During the baseline process and will be encouraged to use the app for the duration of the study. QuitGuide features are listed in Table 1. Participants will be instructed to click "I Was Smoke Free Today" and the "I Slipped" tab to update their status every day (see Figure 1). Participants can use the on-demand "Track My Craving" tab to record and get help with managing cravings. They can click the "Manage My Mood" tab to track their mood and get tips on managing bad moods.

Participants can also personalize the app home screen with their list of reasons for quitting. Clicking the icon on the top right of the home screen will open a summary screen that will help participants to monitor their smoking cessation milestones and money saved by not smoking. Clicking the icon on the top left of the home screen enables modification of the quit plan; setting places and times of day when/where participants would like to receive app messages, and create journal entries. Participants can also click "My History" to examine their mood, urge, and lapse history. Lastly, participants may click "How to Quit" to learn more about ways they can improve their chances of successfully quitting (Figure 1).

[figure not shown]

Figure 1. QuitGuide app home screen

### ***Smart-T + NRT Condition.***

Participants who are randomly assigned to the Smart-T condition will download the Smart-T app and it will be set for a quit date 1 week following the baseline process. Smart-T provides content during the pre-quit period to prepare participants for their quit attempt. Participants will receive information on how to use Smart-T app features at the baseline visit and will be encouraged to use the app for the duration of the study. The Smart-T app contains multiple components including an EMA delivery and data transfer system, automated messages, and on demand content. Each feature is described below.

**Automated messages.** Over 400 unique messages have been created for the Smart-T app and message content has been evaluated by 5 tobacco treatment experts. Similar to our pilot study of the Smart-T app, 4 levels of automated messages will be used for this study (see Table 2). One message will be delivered at the end of each EMA (note: the message will include the participant's first name). Level 0 messages will be pushed during the one week pre-quit period. These messages are not tailored, but rather are delivered in a predetermined order. Message topics are primarily motivational and/or focused on planning and preparing for the quit attempt and benefits of quitting (e.g., "John, Now is the time to create a "smoke free" home environment! Studies show that people who ban smoking in their home increase their chances for quitting"; "John, Sometimes people save a pack of cigarettes (or even a few cigarettes) "just in case" or to prove they have the willpower to not smoke. DON'T! This just makes it easier to start smoking again!");

"John, it's OK to have mixed feelings about quitting. Don't let that stop you! There will be times that you don't feel like quitting! Stick with it anyway!"). Participants will receive level 4 messages during the post-quit period when they indicate that they smoked that day. Level 4 messages attempt to motivate the participant to stop smoking.

**Table 1.** Comparison of treatment conditions.

Components	Smart-T	QuitGuide
Combination NRT	X	X
EMA	X	X (add on for this study)
Set a quit date	Quit date is set to 1 week after the baseline visit	
Smoking cessation psychoeducation	X	X
Treatment messages tailored to currently present lapse triggers	X	
On demand tips and exercises		X
Coping with cravings	X	X
Coping with mood	X	
Coping with stress	X	
Coping with others smoking	X	X
Motivational messages	X	
Benefits of quitting	X	
Harms of smoking	X	
Coping with insomnia	X	
Coping with pain	X	
Scheduled cessation tips		X
Individualized quit plan		X
Record craving/withdrawal	X	X
Record slip	X	X
Record smoking triggers		X
List reasons for quitting		X
Summary of savings from smoking fewer cigarettes		X
Share quit information on social media		X

**Table 2.** Smart-T message types.

[figure not shown]
Type	Conditions for message delivery
Level 0	Pre-quit
Level 1	Post-quit when imminent lapse risk is low.
Level 2	Post-quit when lapse risk is high & following lapse when participant is still interested in quitting.
Level 3	Post-quit immediately following lapse.
Level 4	Post-quit when already smoked that day.

Level 3 messages will be delivered immediately after lapse occurs and these motivational messages will encourage a return to abstinence (e.g., "John, A slip is a sign that you need to improve your smoking cessation plan. Think about what went wrong and develop a stronger plan to stay quit. Keep trying and YOU WILL SUCCEED!"). **On-demand content.** Several Smart-T components are available through the smartphone app 24 hours a day, 7 days a week (see Smart-T pre-quit home screen in Figure 3). First, the "Call Counselor" function/button is programmed to automatically call the free Oklahoma Tobacco Help Line ([name]) so that participants can reach a live counselor at any time (the Smart-T app automatically saves the duration of each Help Line call for future analysis).

Second, the "Quit Tips" function/button links to a menu of treatment related messages (see Figure 4). Third, the "Medications" function/button offers information (e.g., common side effects, quit statistics, use instructions) about NRT medications that will be provided to participants (i.e., nicotine patch and gum/lozenge; see Figure 5).

**Figure 2.** Level 2 messages.

In the Smart-T feasibility study, most participants (83%) used the on-demand Quit Tips and Medication Tips features and participants viewed an average of 31 (median=18) Quit Tips and 15

(median=10)

[figure not shown]

Figure 3. Smart-T pre-quit home screen. Figure 4. Quit Tips function.

Figure 5. Medication function.

Medication tips per viewing session. Participants may have viewed such a high number of tips because they found the information useful and engaging. High participant ratings for helpfulness/ usefulness of the on-demand Tip features adds weight to this explanation.

*Other Smart-T app features.* During the pre-quit period, Smart-T participants will receive a daily message that reminds them of the number of days until their scheduled quit date (e.g., "John, You are scheduled to quit smoking in 5 DAYS at 10:00 pm next Sunday night. Developing a plan to quit and taking your medications will GREATLY increase your chances for staying quit."). Periodically, participants also receive messages to remind them that the on demand features are available when/if needed.

### Description of Study Measures.

**Baseline and Follow-Up Assessments.** Measures will assess demographic and smoking characteristics, multiple constructs that are known to be related to lapse (e.g., depression, stress, affect, social support), and document intervention effects (See Table 3 and Appendix). We will also access participant perceptions of each app feature. The Baseline process will take approximately 60-90 minutes to complete and data will be collected either on laptop/tablet computers using Questionnaire Development System (QDS) software or remotely via REDCap surveys. QDS uses a computer-administered self-interview format (i.e., ACASI), which reduces data entry errors and the need to retain paper copies of raw data. Each item appears on the computer screen while the program simultaneously reads the item (participants touch the screen to select answers only after QDS reads each item). Participants wear headphones so that others do not hear the survey items. Participants from our previous studies in similar populations, including those with no computer experience, have reported few problems using the QDS program. Staff will be available to help participants who may have difficulty. The REDCap surveys have been designed to replicate the QDS version as closely as possible. Up to 30 participants will complete a 16-week qualitative interview with a staff member over the phone regarding their experiences in the study so far. The 26 week post-quit follow-up assessment, which includes a longer EMA (i.e., 20-30 minutes) will be completed by participants in the smartphone application or through REDCap survey. Additionally, up to 100 intervention group participants and up to 100 control group participants will complete a 15-30 minute

qualitative interview with a staff member over the phone (or via REDCap if a medical condition

prevents them from being able to speak for long periods of time) as part of their 26 week post-quit follow-up assessment. Recordings will be transcribed by internal staff, Microsoft Transcribe, or by approved contractors with whom a Business Associates Agreement has been made. When using Microsoft Transcribe, all transcriptions will be reviewed by study staff. Participants will be notified that they will earn a \$5 bonus if they complete the final EMA within the first 24 hours that it is available.

**Ecological Momentary Assessment (EMA)** enables measurement of phenomena in real-time, natural settings. EMA items will identify fluctuations in key variables that predict study outcomes with less bias than traditional in-person assessments. EMA data will be used to identify moments of high smoking lapse risk, tailor Smart-T messages, and examine treatment mechanisms.

**EMA types.** The EMA methodology used in this study will be similar to what has been used in our previous studies, and by other researchers. EMA items will assess multiple **Table 3. Measures.**

MEASURE	ITEMS	FULL BATTERY ASSESSMENTS			EMA
		Screen	Base	26-W	
Screening Questionnaire	22	X			Cigarettes Smoked
Rapid Estimate of Adult Literacy in Medicine-Short Form 	9	X			Social Interactions and support
Weight/Height/CO	5		X		NRT Use
Smoking Status Questionnaire 	2-4		2	4	Side Effect Items
Tobacco History Questionnaire	40		X	20	Alcohol Consumption
Heaviness of Smoking Index 	2		X	X	Sleep Items
Self-Efficacy Scale 	10		X	X	
Demographic/Background Questionnaire	23		X		End of Day Daily Diary‡
Scale of Subjective Social Status	2		X	X	Cigarettes Smoked
Urban Life Stressors Scale 	21		X		Alcohol + Marijuana Use
Center for Epidemiological Studies Depression 	10		X	X	iCO Breath Test (3 times per week)
Perceived Stress Scale 	4		X	X	Weekly App Questions
Pandemic Stress Index (PSI) 	3		X	X	Random/Event EMAs
Interpersonal Support Eval. List 	12		X		
Self-Rated Health 	31		X	10	Recency of Smoking
BRFSS Inadequate Sleep	5		X		Urge to Smoke
BRFSS Adverse Childhood Experience	11		X		Stress
Health Related Quality of Life	3		X	X	Availability of Cigarettes
Patient Health Questionnaire + GAD7	15		X	X	Recent Alcohol Use

constructs that are hypothesized to be related to smoking lapse (see Table 3). Three types of EMAs will be used: daily diary, random sampling, and event sampling. Random and daily diary EMAs will be prompted and initiated by the phone. The phone will ring and vibrate to cue these EMAs for 30-60 seconds. If the participant has not responded after 5 prompts, the EMA will be recorded as missed. Event sampling is initiated by participants. Participants are instructed to self-initiate "Record Cigarette" EMAs during the pre-quit period, and "Lapse" EMAs during the post-quit period. We expect random and event sampling EMAs to take approximately 30 seconds to complete and daily diary EMAs to take approximately 1-2 minutes to complete. All EMAs will be date and time stamped for future analyses.

**Daily diary.** Daily diary EMAs will be completed twice each day for the first 14 weeks of the study and once per day for the last 13 weeks of the study. The phone will initiate the morning daily diary 30 minutes after the participant's pre-set wake time (weeks 1-14) and questions ask about the previous day (e.g., "How many cigarettes did you smoke yesterday?" "Did you use marijuana yesterday?", and "Did you drink any alcohol yesterday?" If the participant answers "yes," he/she will be prompted to indicate the type and quantity of the alcohol/cigarettes that were consumed). In addition, participants will be asked each day if they experienced severe NRT side effects (the app will instruct participants to call 911 if they experience severe NRT side effects, and it will automatically send research staff an encrypted email to contact participants). For the entire 27 weeks of the study, the end of day daily diary will be completed 60 minutes before the

Alcohol Quantity and Frequency Questionnaire 	9		X	X	Cessation Motivation
Alcohol Quantity and Frequency Questionnaire 	9		X	X	Interaction with Smokers
Treatment Quality and Satisfaction Survey	19			X	Social setting/Location
Treatment Quality and Satisfaction Survey	19			X	Reasons for Lapse*
Treatment Improvement Interview 	18			X	Cigarette Reward Value*
Locator Form 	8		X		Lapse Warning Signs*
Financial Strain Questionnaire	9		X		Weekly EMA
MacArthur Major Discrimination	4		X		Pain
Modified Cigarette Evaluation Measure	12		X		Treatment Quality
Short Scale Anxiety Index	5		X	X	HRQoL
Religious Questionnaire	2		X		Readiness to Change
Perceived Neighborhood Disorder and decay	15		X		Sleep
Collective Efficacy	10		X		Smoking Items
Informal Integration with Neighbors	3		X		Pandemic Stress Index
Fear & Mistrust	7		X		Covid Vaccine
Personal Victimization	3		X		
Perceptions of Mobile Phone Intervention Questionnaire	23		X		
Covid Vaccine	5		X	X	
Delay Discounting Task (TOAD)	10		X		
Time needed to complete assessment (minutes)	--	8	60	40	†Note: Daily Diary EMAs also contain all Random EMA items
Note. *Event EMA's only. Screen = Screening; Base = Baseline; 26-W = 26Week Post-Quit Follow-Up.					

participant's pre-set bedtime. If the participant does not respond to the daily diary assessments, they will be rescheduled (up to 2 times) 15 minutes later. A carbon monoxide test will be included as one component of this EMA 3 days each week. Participants will not receive credit for completing the end of day EMA if they do not complete the prompted iCO breath tests. Both the morning and end of day daily diary EMAs will include all random sampling items. Constructs that will be assessed are listed in Table 3 and actual EMA items are presented in the Appendix. Note: During one EMA each week, participants will be asked multiple questions about the usefulness of their app (see Appendix).

*Random sampling.* Participants will be prompted to complete random EMAs, scheduled to occur during each participant's normal waking hours, 3 times each day for 5 weeks (1 week pre-cessation and 4 weeks post-cessation) and 1 time per day for the next 9 weeks (week 6 through 14). Random sampling will not be conducted during weeks 15-27. EMA items will assess the 6 items used for the lapse risk estimator (i.e., urge to smoke, stress, recent alcohol use, interaction with other smokers, cessation motivation, and cigarette availability). Other relevant constructs will also be assessed during random sampling (e.g., recency of smoking, odds of smoking today; See Table 3 and Appendix).

*Event sampling.* All participants will be asked to self-initiate Smoking EMAs (pre-quit week), and Lapse EMAs (post-quit for 26 weeks), see Smart-T pre-quit home screen in Figure 3). Smoking EMAs. During the first week of assessment (pre-quit week), participants will be instructed to indicate when they smoke (by clicking the "Record Cigarette" button). Because the assessment burden would be excessive for heavy smokers if each smoking occasion were assessed, the smartphone will randomly sample up to two smoking occasions from each participant per day. Lapse EMAs. After the quit date, participants will be instructed to complete lapse EMAs (by clicking the "About to Slip" or "Already Slipped" buttons) when relevant. Lapse EMA items are nearly identical to those presented in the random EMAs. However, questions are worded to separately assess the participant's responses immediately prior to AND following the lapse. "About to Slip" EMAs are followed by a second EMA 15 minutes later to assess whether participants actually lapsed. Participants are instructed to complete an "Already Slipped" EMA when they lapsed, but did not complete the "About to Slip" EMA prior to the lapse. Post-lapse EMAs query about the reinforcing value of the lapse cigarette(s), and causes of the lapse. Constructs that will be assessed are listed in Table 3 and actual EMA items are presented in the Appendix.

The mHealth Shared Resource at the OUHSC and Stephenson Cancer Center (SCC) has developed the Insight™ mHealth Platform which empowers researchers to build, test, and launch technology-based assessment and intervention tools. The mHealth resource employs a program manager and 4 senior programmers who develop and maintain web and mobile applications and relational databases. Applications are developed using state-of-the-art cross platform design tools. The Resource is located within the TSET Health Promotion Research Center (HPRC), where [name] office is located. [name] is the Scientific Director of the mHealth Shared Resource, which will provide the programming services for the proposed project.

*Smartphone training.* Participants will watch a brief step-by-step video tutorial (created by the researchers) at the baseline visit that demonstrates use of the app features (i.e., QuitGuide or Smart-T). Additional instructions on how to use the study apps will be loaded into the app home screen so that participants may view them at any time. We have achieved high EMA compliance rates (i.e., 82%-87% of all EMA's completed) using similar protocols in 5 samples of socioeconomically disadvantaged smokers (e.g., homeless smokers, safety-net hospital patients).

**Data loss prevention.** In order to overcome potential loss of data if participants lose their phone (less than 1% of phones have been lost in most studies), phones will be programmed to connect to our secure server each day to upload encrypted data. This will ensure that no collected EMA data are lost. This tactic will also allow the researchers to remotely monitor each participant's EMA completion rate and intervene (e.g., call the participant) when this rate is low (calls will be noted in the dataset and this variable may be used as a covariate in study analyses). Importantly, EMA data are password protected and encrypted on the phone and only encrypted data are transmitted to our secure server. Thus, study data are ONLY accessible by the research team. If a phone is lost, the app and all study data will be remotely wiped and only one replacement phone will be provided to each participant.

**EMA alert settings.** At the baseline visit, a phone set-up wizard is used to set participant sleep and wake times for each day of the week (Note: sleep/wake times can be changed for those with variable schedules). This practice reduces the likelihood that the phone will ring when participants are sleeping. In addition, participants may delay random EMAs by up to 20 minutes (i.e., by clicking the snooze assessment option when an EMA is prompted). Daily diaries will be automatically rescheduled 15 minutes later (two times) if a participant does not respond to the prompt.

**Compensation.** All participants will be compensated \$30 for completing the Baseline assessment and \$50 for completing the Week 26 post-quit follow-up assessment (note: participants who complete the 26 post-quit follow-up EMA within 24 hours will receive a \$5 bonus) and qualitative interview at either the 16-week mark or the 26-week mark. Participants will only be asked to complete 1 qualitative interview and will not be asked to complete both interviews. We will ask all participants to complete interviews until we have completed 30 16-week interviews and a combined 200 26-week interviews (100 per group). Participants will also be compensated monthly via GreenPhire gift cards based upon the percentage of Daily and Random EMAs that were completed. During the first 37 days (~5 weeks) of the study (participants will be prompted to complete 5 EMAs per day). In the first 7 days those who complete 50%-69% of all assessments will receive \$12 in gift cards, those who complete 70%-79% of assessments will receive \$18 in gift cards, and those who complete 90% or more of their EMAs will receive a total of \$25 in gift cards. During the next 30 days, participants will earn up to \$50 per 15-day period (i.e.,  $\geq 90\%$  of EMAs completed = \$50 per 15-day period, 80%-89% = \$36 per 15-day period, 50%-79% = \$24 per 15-day period). During the next 60 days (~9 weeks) of the study (weeks 6-14), participants will be prompted to complete 3 EMAs per day, and will earn up to \$36 per 15-day period (i.e.,  $\geq 90\%$  of EMAs completed = \$36 per 15-day period, 80%-89% = \$28 per 15-day period, 50%-79% = \$18 per 15-day period). During the final 13 weeks of the study (weeks 15-27; participants will be prompted to complete 1 EMA per day), participants will earn up to \$30 per 15-day period depending on the percentage of EMAs completed (i.e.,  $\geq 90\%$  of EMAs completed = \$30 per 15-day period, 75%-89% = \$22 per 15 day period, 50%-74% = \$14 per 15-day period). **PARTICIPANTS WILL NOT BE COMPENSATED FOR ACCESSING ON-DEMAND APP FEATURES OR COMPLETING TREATMENT**

[figure not shown]
**COMPONENTS.** Participants will not receive payment for phone surveys until they confirm or update their contact information (i.e., participants can click a button in the app to confirm/update their contact information, or study staff will attempt to contact them every 15 days to update/confirm contact information). If an interview eligible participant does not complete the 26-week post-quit follow-up assessment (either the phone survey component or the phone call interview component), he/she will be contacted to reschedule and request that loaned phones be returned in person or by mail.

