Participants who complete the in-person baseline visit will: 1) receive combination NRT (i.e., nicotine patch and gum/lozenge), and 2) complete EMAs daily on study provided smartphones. Participants who complete the remote baseline process will be mailed NRT, and a phone (if necessary) to complete EMAs. NRT has been shown to increase successful smoking cessation, and is currently offered via Quitline in all but 5 states. Combination NRT (patch + gum or lozenge) is considered a first line treatment, is relatively low-cost, can be kept on-site for easy distribution to study participants and is more effective than the patch or gum/lozenge alone. Consistent with over-the-counter package labeling, participants will be offered up to 10 weeks of nicotine patches (i.e., label dosage recommendations will be followed) and up to 12 weeks of nicotine gum or lozenges (i.e., participants will receive a 4 week supply of NRT at the completion of the baseline process and will be mailed NRT upon request for post-quit weeks 512).

Participants who own an Android smartphone (OS version 6.0 or higher) will be encouraged to download and use the study app on their own phone. Those who do not own this type of smartphone and those who do not have a data plan will be loaned a Samsung smartphone (or equivalent) for 27 weeks so that they may complete EMAs. Participants will navigate through the EMA program and enter data simply by touching the screen. The study app (i.e., Smart-T app or EMA only app) includes a “Call Staff” function/button that automatically calls study staff (e.g., if they have problems completing EMAs). The EMA app also includes a “Payment” button which, when pressed, indicates the number of EMAs that have been prompted and completed and the current level of compensation based upon the up-to-the-moment percentage of EMAs completed. Smartphones will automatically collect data when on-demand features are accessed for both the QuitGuide and Smart-T groups (e.g., number of times features are used). Use of personal vs. study provided phones will be examined as a covariate in all analyses.

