## Biochemical Assessment of Smoking Status.

Consistent with most published smoking cessation RCTs (see Clinical Practice Guidelines), our

primary study outcome will be biochemically confirmed 7-day point prevalence abstinence 26 weeks following the scheduled quit date. Secondary outcomes (e.g., 30-day point prevalence, time to first lapse, longest time of quit) will also be examined. Smoking abstinence will be measured daily via EMA self-reports and the Bedfont iCO smokerlyzer will be used to verify smoking status on 3 days per week (during the end of day EMA). Participants will be prompted to connect the iCO device to the study smartphone and follow step-by-step directions to complete the iCO test (e.g., hold your breath countdown, exhale countdown; See Figure 8). Results of these tests will be date and time stamped and saved. The Smart-T algorithm will utilize the results of the iCO test to inform the feedback that is delivered at the completion of EMAs. Please note that we have integrated automated and secure (i.e., encrypted) facial recognition software to ensure that only the participant completes prompted iCO tests. Our CO criteria for abstinence is consistent with numerous studies using cutoffs of  $\leq 6$  ppm. The half-life of CO is up to 8 hours depending on a variety of factors (e.g., time of day, daily smoking rate, recency of smoking, physical activity). Studies have shown that expired CO is a valid indicator of smoking status and cessation outcomes and compares favorably with cotinine and other biochemical measures that have longer detection windows. We believe that self-reports of abstinence combined with CO levels suggestive of recent abstinence provide an accurate, immediate, and practical measure of abstinence. Finally, the manufacturer indicates that the iCO is valid for approximately 200 CO tests and has a sensor sensitivity of 1 ppm. Our protocol will require 81 CO testing sessions (3 per week for 27 weeks), allowing for repeated tests when/if needed.

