## E. Statistical Methods

**Aim 1.** We will compare the proportion of participants that are biochemically verified as abstinent (i.e., iCO and self-reports indicate no smoking in the past 7 days) between the treatment conditions (i.e., Smart-T vs. QuitGuide), at 26 weeks post-quit using a chi-square or

Fisher's exact test. We will perform the analysis under the intention to treat (ITT) assumption wherein participants who miss iCO EMAs will be considered not abstinent. We will examine the missing rate and missing patterns before analysis. If the combined missing rate is very small, say less than 5%, then we may safely perform the data analysis on the available data or the data assuming ITT. If the missing rate is high, then we will explore sequential multiple imputation (SMI) as described by Raghunathan et al. The analysis results from SMI data will be compared with those from the available data and ITT analyses. Based upon previous studies of mobile phone based interventions for smoking cessation (see Cochrane Review), we expect that 9% of those receiving the QuitGuide + NRT treatment will be abstinent at the 26 week post- quit follow- up visit, and based upon our pilot work, we expect that 18% of those receiving the Smart-T + NRT treatment will be abstinent at the 26 week post-quit follow-up visit (see). With an alpha of 0.05 and 225 participants in each group, we have 80% power to detect a 9% difference in biochemically confirmed 7-day point prevalence abstinence at 6 months (i.e., 18% abstinent in the Smart-T group vs. 9% abstinent in the QuitGuide group). We expect that groups will be similar in baseline characteristics (e.g., sex, nicotine dependence) due to randomization; however, in addition to the chi-square analysis, we will perform logistic regression to determine if the odds of abstinence vary by other baseline characteristics (e.g., sex, race/ethnicity). Finally, we will examine the interaction between treatment condition and sex (and race) to identify potential differential effects on abstinence. The enrollment/baseline type (e.g., in person vs. phone call) will be included as a potential covariate in analyses.

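### Staff calls triggered by low EMA completion arise after randomisation, yet the plan allows them as a covariate; they should be kept out of the adjusted Aim 1 and Aim 2 arm comparisons

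*Combined protocol and SAP*

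**What the plan says.** The paragraph on data loss prevention (Description of Study Measures) says that daily uploads let the team "remotely monitor each participant's EMA completion rate and intervene (e.g., call the participant) when this rate is low". No level is given for a low rate. It then says that "calls will be noted in the dataset and this variable may be used as a covariate in study analyses". It does not say which analyses, in what form (yes/no, count or timing), or whether comparisons between arms are excluded.

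Three other places bear on what this variable measures:

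- **Endpoint.** Under Biochemical Assessment of Smoking Status, the "primary study outcome will be biochemically confirmed 7-day point prevalence abstinence 26 weeks following the scheduled quit date". The daily diary text says of the end-of-day diary that "A carbon monoxide test will be included as one component of this EMA 3 days each week", and Aim 1 in section E says that "participants who miss iCO EMAs will be considered not abstinent".
- **Arm.** For Smart-T, "One message will be delivered at the end of each EMA". Table 1 lists the EMA in QuitGuide as added on for this study, and Hypothesis 2 contrasts tailored messages with similar QuitGuide situations in which no message is given.
- **Models.** The primary Aim 1 comparison is a chi-square or Fisher's exact test. Section E adds a logistic regression on baseline characteristics (enrollment type is a potential covariate), a GLMM of abstinence over time, and for Aim 2 a linear mixed model and a regression of success percentages. None of these names calls as a covariate, and none rules them out.

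**The concern.** A call is a marker of disengagement during follow-up. Two features make it unsuitable as a covariate in an arm comparison.

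First, arm may influence it. Completing an EMA brings a message in one arm and none in the other, so completion, and hence calling, could differ in either direction.

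Second, it is linked to the recorded outcome, partly by construction. The breath test sits inside an EMA and a missed test is scored as not abstinent. Motivation to quit can also plausibly drive both completion and abstinence.

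Adjusting for such a variable compares called with called and uncalled with uncalled participants. Those groups are no longer balanced by randomisation, and any part of the effect that works through engagement is removed. The adjusted coefficient then does not estimate the effect of assignment to Smart-T. Because use is optional, the choice could also be made after the results are seen.

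**Working it through.** **1. The plan's own figure.** Inputs from section E, Aim 1: 18% and 9% abstinent, 225 per arm, alpha 0.05 (taken as two-sided; the text does not say).

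- Mean proportion 0.135. SE under the null = sqrt(2 × 0.135 × 0.865 / 225) = 0.03222.
- SE under the alternative = sqrt((0.18 × 0.82 + 0.09 × 0.91) / 225) = 0.03194.
- z = (0.09 − 1.96 × 0.03222) / 0.03194 = 0.841, so power = 80.0%, as stated.
- Unadjusted odds ratio = (0.18/0.82) / (0.09/0.91) = 2.22. Risk difference = 9.0 points.

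Calls play no part in this calculation.

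**2. Effect of adding a call indicator.** Large-sample simulation, 2,000,000 records per scenario. Latent motivation is standard normal and balanced by randomisation. It lowers the log odds of a call by 1 per SD and raises the log odds of abstinence by 1 per SD. The call's own coefficient on abstinence is 0, −1 or −2 (−0.5 in the equal-call row). Intercepts fix the call and abstinence rates in each arm. All call rates and association strengths are assumptions.

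| Calls, Smart-T / QuitGuide | True 18% vs 9%: adjusted OR | Standardised risk difference | True 12% vs 12%: adjusted OR |
|---|---|---|---|
| 30% / 50% | 1.64 to 1.94 | 5.2 to 7.3 points | 0.70 to 0.86 |
| 40% / 40% | 2.27 | 9.0 points | 1.00 |
| 50% / 30% | 2.60 to 3.40 | 10.7 to 13.0 points | 1.15 to 1.42 |

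A second set of assumptions (engagement coefficient 1 or 2 on the call) gives:

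- calls 24% vs 42%: OR 1.96, 7.5 points
- stronger engagement link, 30% vs 44%: OR 1.88, 6.7 points
- stronger engagement link, 59% vs 44%: OR 3.05, 11.7 points

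With a call gap of only about 5 points and a weaker link, the OR is 2.15 to 2.33 and the risk difference 8.5 to 9.4 points.

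**3. Check by hand.** In a fitted logistic model with intercept, arm and call, the fitted number abstinent in each arm equals the observed number. If a fraction q of an arm is called, the call odds ratio is c and the arm's abstinence is p, the odds x among the uncalled solve

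(1 − q) · x/(1 + x) + q · cx/(1 + cx) = p,

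and the adjusted OR is x(Smart-T) / x(QuitGuide). Take c = 0.18, the value fitted in the 30% / 50% scenario with call coefficient −1.

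- QuitGuide, q = 0.5, p = 0.09: x = 0.1756, since 0.5 × 0.1494 + 0.5 × 0.0306 = 0.090.
- Smart-T, q = 0.3, p = 0.18: x = 0.3067, since 0.7 × 0.2347 + 0.3 × 0.0523 = 0.180.
- Adjusted OR = 0.3067 / 0.1756 = 1.75, equal to the simulated 1.75.

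With no true effect (12% in both arms), x = 0.2462 for QuitGuide (0.5 × 0.1976 + 0.5 × 0.0424 = 0.120) and x = 0.1869 for Smart-T (0.7 × 0.1575 + 0.3 × 0.0325 = 0.120). The adjusted OR is 0.1869 / 0.2462 = 0.76 (simulated 0.77): an apparent harm where none exists.

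If q is the same in both arms, standardising over q returns each arm's own p, so the risk difference is unchanged. The small move of the OR from 2.22 to 2.27 in that row is non-collapsibility, not bias.

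**The case against.** The strongest reply is that the main result is safe. The primary test takes no covariates, the accompanying logistic regression is described in terms of baseline characteristics, and the wording on calls is only permissive. That stands. A reader might infer from the covariate sentence that the primary comparison is compromised; the documents do not support this.

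A reader might also infer that completion does differ by arm. The documents do not show that either. They give no completion or call rates by arm, and both arms are paid for EMAs on one schedule, which is a strong shared incentive. The Smart-T messages in the pre-quit week are not tailored. A difference by arm is plausible, not established, and the shift needs one.

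The simulation has limits. It does not code the rule that a missed iCO counts as smoking, it gives arm no effect on latent motivation, and it does not model the Aim 2 outcomes. Part of the largest OR shifts is non-collapsibility. The figures show direction and plausible scale only.

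Phone type may look like a parallel problem, since "Use of personal vs. study provided phones will be examined as a covariate in all analyses" and "only one replacement phone will be provided to each participant". No section describes a participant moving from a personal to a loaned phone. The replacement rule concerns lost phones, reported as under 1% in most studies, and the natural reading is status at entry. That extension is not supported. Nor does the lack of a numeric call threshold show unequal handling: no arm-specific rule is stated.

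What remains is an open permission to use a post-randomisation variable in models that compare arms.

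**Conclusion.** The point holds for the supporting and secondary models: the Aim 1 logistic regression, the GLMM of abstinence, and the Aim 2 linear mixed model and regression comparisons. If calls were entered there and call rates differed by arm, the treatment estimate would be biased towards or away from no effect according to which arm is called more, and an apparent effect could arise where there is none. The mechanism is certain enough to act on; the size is not known. Under assumed gaps of 14 to 20 points, an OR of about 2.2 becomes roughly 1.6 to 3.4. At about 5 points the change is trivial, and with equal call rates the risk difference does not move.

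**What to change.** In the data loss prevention paragraph, replace the parenthesis on calls with wording to this effect: calls will be recorded and tabulated by arm as a process measure; they will not be a covariate in any Aim 1 or Aim 2 treatment comparison, where adjustment is limited to variables fixed before randomisation; they may serve as an auxiliary variable in the multiple imputation or in analyses labelled exploratory.

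The cost is a short change of protocol wording. No new data are needed, and the stated sample size and 80% power are unchanged. No change to the phone-type covariate or to the call threshold is needed on this account.
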